Effectiveness of Single Dose Fosfomycin and Single Dose Levofloxacin as Pre-Urodynamic Antibiotic Prophylaxis for Urinary Tract Infection Prevention in Post-Urodynamic Examination

[name]

[name]

[name]

[name]

[name]

NCT Number:

NCT06017479

October 27th, 2022

Department of Urology

RSUPN dr. Cipto Mangunkusumo

Research Title

Effectiveness of Single Dose Fosfomycin and Single Dose Levofloxacin as Pre-Urodynamic Antibiotic Prophylaxis for Urinary Tract Infection Prevention in Post-Urodynamic Examination

Abstract

a) Study aims

This study aims to compare the effectiveness of administering single doses of fosfomycin and levofloxacin pre-procedure on the incidence of urinary tract infections (UTIs) following urodynamic examination.

b) Research Method

This study utilized a single-blinded randomized clinical trial design to compare the proportion of post-urodynamic UTIs in the group receiving single-dose levofloxacin pre-urodynamic versus the group receiving levofloxacin post-urodynamic for three days. The target population consisted of patients undergoing urodynamic examination at RSUPN dr. Cipto Mangunkusumo from November 2022 to August 2023. The total sample size in this study was 100 patients. On the fourth day post-urodynamic, urinalysis and urine culture were performed to determine the diagnosis of UTI. Chi-square test was used to analyze the association between UTI and treatment group. Results were considered statistically significant if $p < 0.05$.

c) Expected Results

The expected results are data regarding the comparison of UTI incidence post-urodynamic examination in the group given single-dose levofloxacin and single-dose fosfomycin prior to urodynamic examination.

d) Outcome

The incidence of UTI in the group receiving single-dose levofloxacin pre-urodynamic compared to the group receiving single-dose fosfomycin pre-urodynamic.

e) Benefits

By obtaining data comparing the effectiveness of single-dose pre-urodynamic levofloxacin and fosfomycin on the incidence of UTIs following urodynamic examination, it can serve as a basis for selecting therapy regimens to prevent post-urodynamic UTIs. This can directly contribute to quality improvement, such as reducing antibiotic resistance rates and cost-saving in service delivery at dr. Cipto Mangunkusumo Hospital

Background

In the field of Urology, urodynamic examination is a functional assessment of the lower urinary tract that is useful for diagnosing the causes of incontinence. The number of these examinations increases by 15-20% annually. Aspects of bladder and urethral function assessed include the filling phase, storage phase, and voiding phase. This examination is invasive and carries a high risk of urinary tract infection (UTI) in patients, hence the need for prophylactic antibiotic use to prevent infection. Previous research by [name] et al. in 2016 stated that the administration of prophylactic antibiotics for 3 days post-urodynamic examination could reduce the incidence of secondary urinary tract infections by 55% compared to placebo. The occurrence of infections and the cost aspect of post-urodynamic prophylactic antibiotic administration are concerns in healthcare provision at [name] General Hospital (RSCM).

Data from the Clinical Pathology Department of RSUPD [name] from July to December 2021 showed that 33% of 415 E. coli urine isolates were sensitive to levofloxacin. During the same period, 84% of 219 E. coli urine isolates were sensitive to fosfomycin. The majority of this data was obtained from inpatients. Considering the good sensitivity of fosfomycin to UTIs, researchers intend to compare the use of fosfomycin with levofloxacin as effective prophylactic antibiotics in patients undergoing urodynamic examination.

Study of Literature

Urodynamic Examination

Urodynamic examination is a functional assessment of the lower urinary tract that objectively demonstrates functional capacity and pathological conditions, thus determining the appropriate treatment according to the type of incontinence.³ Bladder and urethral function is assessed during the filling phase, storage phase, and voiding phase, with several provocative maneuvers such as coughing, sneezing, and laughing used to assess correlation with the patient's clinical symptoms.⁴

Urodynamic examination includes uroflowmetry and measurement of post-void residual urine volume, cystometry, ambulatory urodynamics, videocystometry, and urethral pressure measurement. Uroflowmetry is used as an initial examination to assess urinary dysfunction. Parameters assessed in uroflowmetry include flow rate, maximum flow rate, voided volume, time to maximum flow, flow time, and average flow rate.⁵

Urodynamic Indication

Indications for performing urodynamic examination include patients with obstructive complaints in the lower urinary tract (LUTS) and neurological abnormalities, young men with LUTS complaints, patients with neurological disorders who have neurogenic bladder dysfunction conditions, children with urgency and urgency incontinence occurring outside of sleep, children with persistent diurnal enuresis, children with spinal nerve disorders, patients with neurological disorders with incongruity between symptoms and clinical findings, patients with persistent LUTS under appropriate/correct therapy, patients at high risk of complications from a planned therapy, situations where therapy decisions are unclear and require more specific diagnosis confirmation, patients with recurrent incontinence and planned surgery, patients with mixed incontinence of stress and urgency types and those with urinary disorders.⁶

Generally, urodynamic examinations use water/saline solution as a medium to fill the bladder. Multichannel urodynamic examinations are more complex and can be used to measure data that can complement information beyond routine urodynamic assessments of the bladder and abdomen, such as abdominal leak-point pressure (ALPP) and electromyography (EMG). The most advanced form of urodynamic examination is videourodynamics, which is equipped with static cystography and voiding cystourethrography using radiological contrast.^{4,7}

UTI Classifications

Urinary tract infection (UTI) is an infection that occurs in the urinary tract, including the kidneys, ureters, bladder, and urethra. According to the EAU guidelines, UTIs are classified into uncomplicated UTIs, complicated UTIs, recurrent UTIs, catheter-associated UTIs, and urosepsis (Table 1)⁸. Based on location, urinary tract infections can be divided into two categories: upper

UTIs, which involve the kidneys and ureters, and lower UTIs, which involve the bladder and urethra.⁹

Table 1. UTI Classifications⁸

| UTI Classifications | |
|----------------------------|--|
| Non-complicated UTI | Acute, sporadic, or recurrent infections in the upper and/or lower urinary tract affecting non-pregnant women, postmenopausal women without anatomical abnormalities and comorbidities in the urinary tract. |
| Complicated UTI | All UTIs that cannot be classified as uncomplicated. In other words, UTIs in patients with a higher risk of complications, such as: men, pregnant women, patients with anatomical or functional abnormalities in the urinary tract, and/or with other underlying immune disorders such as diabetes or HIV. |
| Recurrent UTI | Uncomplicated and/or complicated recurrent UTIs with a frequency of at least 3 times per year or 2 times in the last 6 months. |
| Catheter-related UI | Catheter-associated UTIs refer to UTIs that occur in patients who use catheters regularly and have used a catheter for at least the past 48 hours. |
| Urosepsis | Urosepsis is defined as life-threatening organ dysfunction resulting from dysregulation of the host response to infection originating from the urinary tract and/or male reproductive organs. |

And these followings are the common terminology used to describe UTI clinically.¹⁰

| Terminology | Definition |
|--------------------------|---|
| Pyuria | Presence of more than 10 white blood cells/mm ³ per large visual field |
| Bacteriuria | More than 10 ⁵ colony-forming of urinary pathogens units per mL |
| Confirmed UTI | Pyuria accompanied by bacteriuria |
| Asymptomatic bacteriuria | Presence of bacteriuria in the absence of genitourinary symptoms or signs |

Diagnostic Evaluation

Diagnosing UTIs can be established through a focused assessment of lower urinary tract symptoms such as dysuria, frequency, and urgency. Diagnostic tests for UTIs consist of three main examinations: dipstick urinalysis, microscopic urinalysis, and urine culture. Urine culture is utilized for patients suspected of acute pyelonephritis, patients whose symptoms do not improve or have recurrent symptoms within 2-4 weeks after completion of treatment, women with atypical symptoms, pregnant women, and male patients suspected of UTI.¹⁰

Urinary Tract Infections after Urodynamic Testing

Previous studies have reported that the incidence of UTIs following urodynamic examination ranges from 1% to 30%. Another study mentioned that urodynamic testing without prophylactic antibiotic use has a bacteriuria incidence of 4-9%.¹¹ In previous research, prophylactic antibiotics were administered 1 hour before urodynamic examination.

Levofloxacin for Pre-Urodynamic UTI Prevention

Levofloxacin is a fluoroquinolone antibiotic with broad-spectrum activity against both Gram-positive and Gram-negative bacteria, as well as atypical pathogens. Levofloxacin exhibits antimicrobial effects against *Streptococcus pneumoniae*, both penicillin-susceptible and penicillin-resistant strains.¹² Previous studies have noted an increasing resistance of Gram-negative bacilli to quinolones.¹¹

Fosfomycin for Pre-Urodynamic UTI Prevention

Fosfomycin is a bactericidal antibiotic with activity against several Gram-positive and Gram-negative bacteria, including vancomycin-resistant enterococci, methicillin-resistant *Staphylococcus aureus*, and carbapenem-resistant Enterobacteriaceae.¹³ Research indicates that *Escherichia coli* and *Enterococcus faecalis* have high susceptibility to fosfomycin.¹⁴ Single-dose oral fosfomycin 3 grams shows peak urine concentration within 4 hours and remains high (>128 mg/L) for 24 to 48 hours, sufficient to prevent pathogens in the urinary tract.¹¹

[figure not shown]
Research Methodology

This study is an experimental research with a single-blinded randomized clinical trial design to compare the proportion of UTIs in patients receiving a single dose of 500 mg levofloxacin and patients receiving a single dose of 3 grams fosfomycin one hour before urodynamic examination. Treatment group allocation was determined using block randomization technique.

This study utilizes a single-blinded design because the outcome assessed in this study is objective urinalysis. The urinalysis evaluator is unaware of the drug regimen received by the research subjects.

UTIs will be assessed based on bacteriuria conditions evaluated within 4 days post-urodynamic using urinalysis examination.

Conceptual Framework

Picture 1. Conceptual Framework

Definition of Work

1. Single Dose of Levofloxacin
A single dose of levofloxacin is defined as the administration of 500 mg of levofloxacin one hour before urodynamic examination.
2. Single Dose of Fosfomycin
A single dose of fosfomycin is defined as the administration of 3 g of fosfomycin one hour before urodynamic examination.
3. Urinary Tract Infection (UTI)
Urinary tract infection is defined based on urinalysis results showing any of the following conditions: leukocyturia (presence of >5 leukocytes/HPF), positive bacteria, positive nitrites, and/or positive leukocyte esterase.
4. Urodynamic
Urodynamic examination in this study consists of non-invasive uroflowmetry, post-void residual volume (PVR) measurement, and cystometrography (CMG) measurement.

Research Hypothesis

The administration of single-dose fosfomycin pre-urodynamic examination is more effective than single-dose levofloxacin pre-urodynamic examination in preventing UTIs.

Source

The data source for this research is primary data collected from patients with indications for urodynamic examination at the urology clinics of RSUPN [name], RS Persahabatan, and RS Siloam Asri from November 2022 to August 2023.

Number of Samples

The sample size calculation is based on the 'Fundamentals of Clinical Research Methodology' regarding proportion calculation for 2 independent groups. Based on literature, the effectiveness of levofloxacin antibiotic against post-urodynamic bacteriuria incidence is believed to have a 20% difference from P2 (P1=0.7) because the effectiveness of fosfomycin against post-urodynamic bacteriuria incidence is 0.9 (P2).¹¹

$$n_1 = n_2 = \frac{[Z\alpha\sqrt{2PQ} + Z\beta\sqrt{P_1Q_1 + P_2Q_2}]^2}{(P_1 - P_2)^2}$$

where $P = \frac{1}{2}(P_1 + P_2)$ and $Q = 1-P$

$$n_1 = n_2 = \frac{[1,96\sqrt{2x0,8x0,20} + 0,842\sqrt{0,7x0,3 + 0,9x0,1}]^2}{(0,7 - 0,9)^2} =$$

$n_1=n_2 = 61,5 \sim 62$ patients for each group

Considering the possibility of drop-out, it was decided to take a total sample of 126 patients, with 63 patients in each group, who will then undergo screening for eligibility and will be randomized equally.

Data Collection Technique

The data collection technique employs consecutive sampling method until the required number of subjects is reached.

Inclusion and Exclusion Criteria

The inclusion criteria for this study are:

- Male/female patients aged >18 years who have indications for urodynamic testing
- Willing to participate in the study

The exclusion criteria for this study are:

[figure not shown]
- Allergy to levofloxacin
- Allergy to Fosfomycin
- Pregnancy
- Uncontrolled diabetes mellitus
- Urinary catheterization
- History of UTI prior to urodynamic testing, based on clinical symptoms and urine examination results
- Refusal to participate in the study

Statistical Analysis Technique

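### The outcome called UTI is defined on urine markers alone, so the trial could not tell asymptomatic urine findings from clinical infection

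*Combined protocol and SAP*

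**What the plan says.** The Abstract, under d) Outcome, only names the outcome: "The incidence of UTI in the group receiving single-dose levofloxacin pre-urodynamic compared to the group receiving single-dose fosfomycin pre-urodynamic". The operative definition is item 3 of Definition of Work: "Urinary tract infection is defined based on urinalysis results showing any of the following conditions: leukocyturia (presence of >5 leukocytes/HPF), positive bacteria". A nitrite or esterase result also counts. Any one of these findings is enough.

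The two statements on assessment are also laboratory-only. Research Methodology says: "UTIs will be assessed based on bacteriuria conditions evaluated within 4 days post-urodynamic using urinalysis examination". The Abstract, under b) Research Method, adds culture: "On the fourth day post-urodynamic, urinalysis and urine culture were performed to determine the diagnosis of UTI". The only outcome analysis, in Statistical Analysis Technique, is a chi-square test of UTI by treatment group.

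Three other places treat symptoms as relevant to UTI:
- The terminology table that follows Table 1 gives asymptomatic bacteriuria its own entry: "Presence of bacteriuria in the absence of genitourinary symptoms or signs".
- Diagnostic Evaluation says: "Diagnosing UTIs can be established through a focused assessment of lower urinary tract symptoms such as dysuria, frequency, and urgency".
- One exclusion criterion reads: "History of UTI prior to urodynamic testing, based on clinical symptoms and urine examination results".

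Two places point the other way. The same terminology table defines Confirmed UTI as pyuria together with bacteriuria, with no symptom required. Diagnostic Evaluation goes on to name three main tests, all of them laboratory tests.

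**The concern.** UTI is judged on symptoms plus urine results at entry, but on urine results alone at outcome. A patient with a positive marker and no complaint is scored the same as a patient with fever and new dysuria. Settling on one urine marker or one culture threshold would not change this.

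The title, the aim and the hypothesis all speak of UTI. The Abstract, under e) Benefits, offers the result as a basis for choosing regimens that prevent UTI after urodynamics. The sample size, however, rests on bacteriuria incidence. A positive trial would show fewer abnormal urine results and be reported as fewer infections. Symptoms not recorded at the time cannot be reliably recovered later, so the gap cannot be closed at the analysis stage.

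**Working it through.** **1. The plan's own figure.** Number of Samples gives effectiveness P1 = 0.7 (levofloxacin) and P2 = 0.9 (fosfomycin) against bacteriuria, with Z values 1.96 and 0.842. With P = 0.8 and Q = 0.2:

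n = [1.96 × √(2 × 0.8 × 0.2) + 0.842 × √(0.21 + 0.09)]² / 0.2² = (1.1087 + 0.4612)² / 0.04 = 61.6

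The plan states 61.5. Both round up to 62, and the plan takes 63 per arm. The figure reproduces, but for bacteriuria and not for clinical infection.

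**2. Expected urine-positive patients.** Reading effectiveness as freedom from bacteriuria, the rates are 30% and 10%: 63 × 0.30 = 18.9 and 63 × 0.10 = 6.3. These are bacteriuria rates. The outcome accepts any of four markers, so its actual rates may differ.

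**3. Symptomatic patients.** The documents give no symptomatic share. I assume 20% to 50%, the same in both arms:
- 20%: 18.9 × 0.20 = 3.8 versus 6.3 × 0.20 = 1.3
- 50%: 18.9 × 0.50 = 9.5 versus 6.3 × 0.50 = 3.2

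That is about 4 to 9 versus 1 to 3 patients.

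**4. What the planned analysis cannot separate.** Take 19 versus 6 positives. Suppose 9 versus 3 of them are symptomatic: the difference of 13 is then 6 symptomatic and 7 asymptomatic patients. Suppose instead 3 versus 3 are symptomatic: the asymptomatic counts are 16 versus 3, and all 13 of the difference is asymptomatic. Both cases give the same two-by-two table and the same chi-square result. The counts are illustrative.

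**5. Power for a symptomatic outcome at 63 per arm.** Power = Φ(z), with z = [|P1 − P2| × √n − 1.96 × √(2PQ)] / √(P1Q1 + P2Q2). At the planned 30% versus 10% this gives 80.9%.
- Share 50% (15% versus 5%): z = (0.794 − 0.832) / 0.418 = −0.09, power 46%. For 80% power, 141 per arm would be needed.
- Share 25% (7.5% versus 2.5%): power 25%, with 298 per arm needed.

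The Abstract gives a total of 100 patients, not 126. With 50 per arm, power at a 50% share is 38%. On either total, a symptomatic outcome can only be described.

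**The case against.** **The laboratory outcome is a reasoned choice.** Research Methodology justifies the single-blind design by the objectivity of urinalysis and describes only the urinalysis evaluator as unaware of the regimen. Self-reported symptoms would lack that protection, and many of these patients have lower urinary tract symptoms before the test. This stands as a reason to keep the urine outcome primary. It does not let that outcome speak for clinical infection.

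**The definition is open.** Definition of Work states what is counted, so a careful reader is not misled. That is true of the protocol, but the title, hypothesis and stated use still speak of UTI.

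**Stronger readings that the documents do not support.**
- A reader might infer that the protocol's own terminology requires symptoms for UTI. It does not do so consistently: an asymptomatic patient with pyuria and bacteriuria fits both Confirmed UTI and asymptomatic bacteriuria.
- A reader might infer that every asymptomatic positive is asymptomatic bacteriuria. Isolated leukocyturia, nitrite or esterase findings do not meet the table's threshold of more than 10⁵ colony-forming units per mL.
- A reader might infer that half to four fifths of the reported UTIs would be asymptomatic. That is only one minus the assumed share.
- A reader might infer that nobody asks about symptoms before the test. The exclusion criterion implies some assessment. What is missing from the legible text is a structured record to compare with day 4. The two figures that are not shown might also contain one.

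**Conclusion.** The point holds as a cheap improvement, not as a fault that invalidates the comparison. On the legible text, the outcome has no symptom component and no post-procedure symptom record is planned. The trial could therefore support a conclusion about urine findings but could not show how much of any difference is clinical infection.

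The size is uncertain. About 4 to 9 versus 1 to 3 symptomatic patients rests on three assumptions: the planning rates for bacteriuria apply to the broader outcome, 20% to 50% of positives are symptomatic, and that share is equal between arms. None of the three is established by the documents. The main conclusion, that the two kinds of difference cannot be separated, needs none of them.

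A reader might go further and hold that every claim about preventing UTI must rest on the symptomatic outcome. With about 46% power even at a 50% share, that would leave the stated hypothesis all but untestable. It is more workable to report the two results side by side.

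**What to change.** 1. Keep the urine-based outcome as primary and name it for what it measures, for example post-urodynamic bacteriuria or urinalysis abnormality.
2. Record dysuria, frequency, urgency, suprapubic pain and fever shortly before the procedure, extending the assessment that the exclusion criterion already implies. Record the same five items again at the day-4 urine collection.
3. Add a descriptive secondary outcome by arm: symptomatic UTI, meaning urine-positive plus at least one new or worsened symptom compared with the pre-procedure record.
4. Word the primary conclusion as one about urine findings, with the symptomatic result beside it.

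The cost is a five-item checklist at two time points, one table and a change of wording. The sample size does not change. The documents describe urine tests on day 4 but not an interview, so a brief contact may have to be added. Two limits should be stated: events will be few, so the secondary outcome is for description only; and symptoms are self-reported, while only the urinalysis evaluator is described as unaware of the regimen. If symptoms cannot be collected, items 1 and 4 (without the symptomatic result) still remove the overstatement.

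### The only outcome, UTI, is defined in two incompatible ways: any one urinalysis marker in the formal definition, bacteriuria in the methods sentence and the sample size

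*Combined protocol and SAP*

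**What the plan says.** The combined protocol and SAP describes the outcome in these places.

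- **Definition of Work, item 3.** This is the only formal definition of UTI: a urinalysis "showing any of the following conditions: leukocyturia (presence of >5 leukocytes/HPF), positive bacteria, positive nitrites, and/or positive leukocyte esterase". Any one of the four findings is enough.
- **Research Methodology.** "UTIs will be assessed based on bacteriuria conditions evaluated within 4 days post-urodynamic using urinalysis examination". The blinding rationale just before it calls the outcome an objective urinalysis and adds: "The urinalysis evaluator is unaware of the drug regimen received by the research subjects".
- **Number of Samples.** The two planning values concern bacteriuria: "the effectiveness of levofloxacin antibiotic against post-urodynamic bacteriuria incidence is believed to have a 20% difference from P2 (P1=0.7" and "the effectiveness of fosfomycin against post-urodynamic bacteriuria incidence is 0.9 (P2". They lead to 62 per group, raised to 63 per group (126 in total) for drop-out.
- **Statistical Analysis Technique.** A chi-square test relates UTI occurrence to treatment group at p < 0.05. There is no definition and no cross-reference to item 3.
- **Abstract b) Research Method.** "On the fourth day post-urodynamic, urinalysis and urine culture were performed to determine the diagnosis of UTI". No rule is given for combining the two tests. The same paragraph describes a different comparison ("versus the group receiving levofloxacin post-urodynamic for three days") and a different size ("The total sample size in this study was 100 patients").

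The literature section also gives a culture count above 10^5 per mL for bacteriuria, but only as common terminology, not as this trial's endpoint.

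**The concern.** Bacteria on urinalysis is one of item 3's four markers, so bacteriuria is a subset of item 3. The two part company for patients who have leukocytes, leukocyte esterase or nitrites without bacteria. Item 3 counts them as events. The methods sentence and the sizing do not.

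This is the trial's only outcome and only test. Two analysts who both follow the plan could build different 2x2 tables from the same patients, and one table could be significant while the other is not. If the choice were left until results are known, the 5% error rate would no longer hold. Separately, a sample size derived for one endpoint says nothing definite about the power for a broader one.

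**Working it through.** **1. The plan's own figure.** Inputs from Number of Samples: P1 = 0.7, P2 = 0.9, mean 0.8, Zα = 1.96 (two-sided 5%), Zβ = 0.842 (80% power, implied rather than stated).

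n = [1.96·√(2·0.8·0.2) + 0.842·√(0.7·0.3 + 0.9·0.1)]² / (0.2)² = (1.1087 + 0.4612)² / 0.04 = 61.6, rounded up to 62.

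The plan prints 61.5 and also rounds to 62. The arithmetic is sound, for bacteriuria.

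**2. Assumptions for the illustration.** None of these stands in the documents.

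- 0.7 and 0.9 mean 30% bacteriuria with levofloxacin and 10% with fosfomycin.
- Every bacteriuric patient is positive under item 3.
- A share f of the non-bacteriuric patients is positive on another marker.
- 63 per group are analysed with a two-sided 5% Pearson chi-square test without continuity correction.

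**3. Item 3 rate.** In each arm the rate is p + (1 − p)·f. For f = 10% in both arms: 0.30 + 0.70·0.10 = 37% and 0.10 + 0.90·0.10 = 19%.

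**4. Power, sample size and disagreement.** Power is exact, by enumerating all outcomes. Sample size uses the protocol's formula with the item 3 rates. Disagreement is the probability that exactly one of the two tests gives p < 0.05 on the same patients. It comes from the joint distribution in each arm: item 3 count = bacteriuria count + Binomial(63 − bacteriuria count, f).

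| f, levofloxacin / fosfomycin | Item 3 rates | Power at 63 per group | n per group | Disagreement |
|---|---|---|---|---|
| 0 / 0 (bacteriuria) | 30% / 10% | 82% | 62 | – |
| 5% / 5% | 33.5% / 14.5% | 72% | 79 | 15% |
| 10% / 10% | 37% / 19% | 62% | 97 | 24% |
| 20% / 20% | 44% / 28% | 47% | 141 | 38% |
| 10% / 5% | 37% / 14.5% | 84% | 59 | 12% |
| 20% / 10% | 44% / 19% | 87% | 54 | 15% |
| 5% / 10% | 33.5% / 19% | 46% | 144 | 36% |

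The ranges quoted elsewhere are across these six scenarios. They are not bounds: more unequal splits would widen them.

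**5. No true difference.** With 20% bacteriuria in both arms and f = 5%, 10% or 20% in both, each test alone has an error rate of 4.8% to 5.2%. The chance that at least one of the two is significant is 7.0%, 7.7% or 8.5%.

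**The case against.** The strongest answer is that item 3 governs. It is the only text that formally defines UTI, and the blinding rationale describes the outcome as urinalysis in general, which fits item 3. UTI occurrence in the analysis paragraph would then most naturally mean item 3. Much of this stands, and it makes item 3 the likelier reading. It does not end the matter. The methods sentence also says how UTI is assessed and names only bacteriuria, and nothing in the readable text ranks one above the other. If item 3 does govern, the sizing still belongs to a narrower endpoint.

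It is also fair to say that the figures are only illustrative. The shares of extra positives are assumed. So is the reading of 0.7 and 0.9 as 30% and 10% bacteriuria, and it sits badly with the 4–9% bacteriuria without prophylaxis given in the literature section, which cites the same reference as the planning values. The contradiction in the text needs none of these figures.

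A reader might infer that culture is a third competing definition. The support is weak. Only the abstract mentions culture for this trial, and that abstract describes another comparison and 100 patients. The readable methods, definition, sizing and analysis sections plan no culture, although the conceptual framework and flowchart are not shown.

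**Conclusion.** The plan is wrong as written. Item 3 conflicts with the methods sentence and with the basis of the sample size, and even on the reading kindest to the plan the 62 per group and implied 80% power are not established for the endpoint tested. As this is the sole outcome, it must be corrected.

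Under the stated assumptions, power under item 3 is 46% to 87% in the six scenarios, against 82% for bacteriuria. The significance verdicts differ in 12% to 38% of trials. If the definition were chosen after results are seen, the false-positive risk would be 7.0% to 8.5% instead of about 5%.

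Three stronger conclusions might be drawn, and the documents support none of them.

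- *The verdict always turns on the definition.* In these scenarios the two definitions agree in 62% to 88% of trials, and disagreement here means significant versus not significant, not a reversed direction.
- *Item 3 leaves the trial underpowered.* Power falls in four scenarios and rises in two. The direction depends on how extra positives split between the arms, which the documents do not give.
- *The definition will be chosen after the results.* Nothing in the documents says so. The point is only that the plan does not rule it out.

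A smaller inconsistency goes with this one: the methods section assesses within four days, the abstract on the fourth day.

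**What to change.** Before any unblinded analysis, name one primary endpoint and use it in the abstract, methods, item 3, sample size and chi-square paragraph. Either choice is defensible.

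- **(a) Bacteria on urinalysis as primary**, with the threshold for a positive result stated, and the item 3 composite as secondary. Suggested wording: *Primary endpoint: positive bacteria on urinalysis (threshold stated) on the specified assessment day, read by an evaluator unaware of the drug regimen. Secondary endpoint: any-marker urinalysis composite (item 3).* No extra test is needed, since item 3 already includes bacteria on urinalysis. The drawback is fewer events than under the composite.
- **(b) Item 3 as primary.** State that 0.7 and 0.9 are bacteriuria figures, and that the sample size and its implied 80% power do not apply to item 3 unless recalculated on item 3 rates. The cost is a justified set of rates and possibly a different size (54 to 144 per group in the scenarios above).

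Under either option:

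- State one assessment day, reconciling the methods section with the abstract.
- State how bacteriuria was measured in the source of 0.7 and 0.9. If it was by culture, the sizing under (a) also needs fresh justification.
- Correct the abstract, and say whether culture is done and whether it has any role in the endpoint.
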